However, food pantries are not a long-term solution to improve health for food insecure people with T2D. Most food pantries do not provide food of sufficient dietary quality to support a healthy lifestyle, particularly for vitamins A and C and calcium.²² Current food pantry clients' diet quality is insufficient for caloric intake, fruits, vegetables, and dairy.²³

Diabetes self-management education (DSME) is an approach with documented efficacy in helping people manage T2D. DSME supports informed decision-making, encourages goal setting and problem solving, and improves self-care behaviors.²⁴ Across many populations, DSME improves glycemic control,²⁵ lowers body mass index (BMI),²⁶ improves diabetes knowledge,²⁷ diet quality,²⁸ physical activity,²⁹ and self-efficacy;²⁷ reduces health care costs and hospitalizations,^{30,31} and increases use of primary care and preventive services.³²

Recent studies have shown promise for DSME among food pantry clients with T2D. One study paired DSME classes with T2D-appropriate food boxes distributed at food banks and found significant improvements in glycemic control.³³ However, this study suffered from problems with attendance and retention, retaining only 42% of participants. In a follow-up trial, only 20% engaged fully with the DSME and food box intervention (i.e., picked up ≥ 9 of 11 food distributions, attended 2 DSME classes, etc.).³⁴

By removing barriers to attendance and retention, our research team will leverage the full potential of home-delivered T2D-appropriate food boxes paired with DSME. We have

Title: Delivering Health: An Integrated Approach to Address Diabetes in the Context of Food Insecurity

PI: [name]

successfully adapted diabetes education for delivery in community settings, including homes, faith-based organizations, and community centers.³⁵ We have adapted DSME for people from diverse cultural backgrounds who face economic, transportation, health care, and health literacy barriers.³⁶ We are experienced at developing interventions to improve health of low-income food insecure people, including food pantry interventions to improve access to healthy food.^{37,38}

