"Participants will be offered a \$40 gift card for participation in each of the two data collection events for a total of \$80. Those participants who only participate in the survey or biometric data collection will receive \$20 for their time. Participants will also be offered \$10 gift cards at each of the dietary recall phone interviews for a total of \$60. Participants will only receive gift cards for the data collection events they complete. If a participant drops out, the study team will document who dropped out and why the drop out occurred. Participants will be able to choose a Tango electronic gift card at each of the data collection events.

Study Population

Up to 110 study participants will be recruited from food pantries located in Benton and Washington Counties in northwest Arkansas.

Inclusion Criteria

- 18 years of age or older
- Food insecure (confirmed with adapted 10-item screener)
- HbA1c levels of ≥ 7

Title: Delivering Health: An Integrated Approach to Address Diabetes in the Context of Food Insecurity

PI: [name]

Exclusion Criteria

- Conditions making it unlikely the participant will be able to follow the protocol, such as terminal illness, non-ambulatory, severe mental illness, severely impaired vision or hearing, eating disorder, or plans to move out of the geographic region
- Pregnant
- Only one adult per household will be enrolled

Risks and Benefits

A risk to study participants is the potential for loss of confidentiality of study data. Measures to protect the confidentiality of study data will be implemented as described in the Data Handling and Recordkeeping section below.

A finger stick is required to collect a small amount of blood for testing, this may cause some discomfort.

The food box deliveries will be packaged to hold the correct temperature of perishable foods for three hours. After that time, or if the box is in any way damaged there is a risk of potentially eating spoiled foods from the food box delivery. There is also a risk of consuming a food item that the participant is unknowingly allergic to. We will do our best to ensure the integrity of the food box deliveries and are always available to contact with any questions regarding the food items in the deliveries.

Potential benefits include provision of nutritionally balanced food to participant's home for the 12 week period of the study. Participants may experience improved health status, specifically related to type 2 diabetes.

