In addition to the potential of benefits to the participants, knowledge gained from the study could potentially benefit patients in the future.

Data Handling and Recordkeeping

The Principal Investigator will carefully monitor study procedures to protect the safety of research subjects, the quality of the data and the integrity of the study.

All study subject material will be assigned a unique identifying code or number. The key to the code will be stored in a secure location in the Office of Community Health and Research. Only the principal investigator and the study coordinator will have access to the code and information that identifies the subject in this study. During data collection events survey data will be collected on a UAMS iPad or laptop using REDCap mobile app (with built in encryption technology). As soon as the data collectors return to UAMS, they will upload the data to the REDCap instance housed on a secure UAMS server and delete the data from the iPad or laptop. Blood specimens collected for HbA1c testing are only used for point of care testing, they will be discarded immediately after the test is performed. At the conclusion of the study the key to the code will be shredded, the data will be permanently de-identified.

Title: Delivering Health: An Integrated Approach to Address Diabetes in the Context of Food Insecurity

PI: [name]

The study will comply with UAMS Admin Guide Policy 3.2.01 – research data, reports and analyses be retained for seven years after final reporting or publication of a project, or longer if required by a sponsor or regulation.

Data Analysis

Analyses will be performed with SAS 9.4. Data will be examined for distributional normality and outliers prior to analyses. Descriptive statistics will be generated for all variables of interest. We will examine patterns and predictors of missing values. If the percentage of missing values is larger than approximately 10%, we will compare models using multiple imputation with those using complete case analysis to examine the potential impact of missing values on the results.

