To examine the intervention's effect on the primary outcomes of glycemic control as measured by HbA1c and diet quality as measured by Healthy Eating Index-2015 (HEI) scores, we will use mixed effects regression models for repeated measures. These analyses will focus on testing for a statistically significant difference between pre-intervention versus post-intervention measures. Additional analyses will include relevant covariates such as sex or age. We will also explore models that include process indicators of dosage of intervention received (e.g., number of food boxes received) to examine whether dosage predicts change in primary outcomes.

Ethical Considerations

This study will be conducted in accordance with all applicable government regulations and University of Arkansas for Medical Sciences research policies and procedures. This protocol and any amendments will be submitted and approved by the UAMS Institutional Review Board (IRB) to conduct the study.

The formal consent of each subject, using the IRB-approved consent form, will be obtained before that subject is submitted to any study procedure. All subjects for this study will be provided a consent form describing this study and providing sufficient information in language suitable for subjects to make an informed decision about their participation in this study. The person obtaining consent will thoroughly explain each element of the document and outline the risks and benefits, alternate treatment(s), and requirements of the study. The consent process will take place in a quiet and private room, and subjects may take as much time as needed to make a decision about their participation. Participation privacy will be maintained and questions regarding participation will be answered. No coercion or undue influence will be used in the consent process. This consent form must be signed by the subject and the person obtaining the consent. A copy of the consent will be given to the participant, and the informed consent process will be documented in the research record.

A \$40 Walmart gift card will be provided to the participant each time they complete a data collection event. If they complete both data collection events, they will receive a total of \$80 in Walmart gift cards.

Dissemination of Data

Title: Delivering Health: An Integrated Approach to Address Diabetes in the Context of Food Insecurity

PI: [name]

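### The only stated missing-data check, multiple imputation against complete cases, could wrongly reassure if people who leave gained less; a delta-adjusted analysis would close the gap cheaply

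*Combined protocol and SAP*

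**What the plan says.** The Data Analysis section gives two steps for missing data. The first is descriptive: "We will examine patterns and predictors of missing values". The second applies only above roughly 10% missing: "we will compare models using multiple imputation with those using complete case analysis", in order to see what missing values could do to the results. No imputation model, auxiliary variables or rule for reading a difference is given. No analysis allows missingness to depend on the unseen outcome.

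For the two primary outcomes, HbA1c and HEI-2015, the same section states that "we will use mixed effects regression models for repeated measures". It does not say that the model uses all enrolled participants. Boxes received enters only exploratory models of change.

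On dropout, the compensation paragraph in Study Design and Procedures says that "the study team will document who dropped out and why the drop out occurred", with no analytic use attached. The Collect data item schedules outcomes before and after the intervention only. The sample size paragraph describes a single-arm design and gives no expected retention.

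Background and Rationale says of an earlier programme with food boxes distributed at food banks that "this study suffered from problems with attendance and retention, retaining only 42% of participants". It presents home delivery as the answer to that problem: "By removing barriers to attendance and retention, our research team will leverage the full potential of home-delivered T2D-appropriate food boxes".

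**The concern.** A participant lost before follow-up contributes a baseline value and nothing else on the outcome. Complete-case analysis ignores that person. Standard multiple imputation, and a likelihood-based mixed model, fill the gap with the response of completers who have the same covariates. None of the three can see that leavers did worse than comparable stayers. Setting one against another tests whether missingness depends on the modelled covariates. It does not test whether missingness depends on the missing outcome.

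With one arm there is no comparison group in which such bias could partly cancel, so it passes straight into the pre-post estimate. If disengaged people gain less and also leave, the average change among all enrolled is overstated, and the planned comparison may give no warning.

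**Working it through.** **Inputs from the sample size paragraph.** HbA1c gain 0.6; SD 1.5; r = 0.5; n = 100; two-sided alpha 0.05; 80% power at d = 0.28.

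**The plan's own figure.** SD of change = 1.5 x sqrt(2 x (1 - 0.5)) = 1.5, so the paired effect size equals d. Detectable d = (1.960 + 0.842)/sqrt(100) = 0.280, or 0.283 with the exact t distribution. The stated 0.28 reproduces.

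**Assumptions not in the documents.** Completers change by -0.6 and dropouts by 0 on average. Residual SD is equal in both groups. Data are normal with baseline mean 9, without truncation at the entry limit of 7. In the main case, dropout is unrelated to baseline and imputation regresses post on baseline.

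**True mean change of all enrolled** = -0.6 x retention. For example, -0.6 x 0.42 = -0.252.

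**Simulation** (1,500 trials of 100 per retention rate, 20 imputations each):

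| Retention | True, all enrolled | Complete case | Multiple imputation | Approximate bias |
|---|---|---|---|---|
| 90% | -0.540 | -0.589 | -0.590 | 0.05 to 0.06 |
| 80% | -0.480 | -0.602 | -0.602 | 0.12 |
| 60% | -0.359 | -0.608 | -0.610 | 0.24 to 0.25 |
| 42% | -0.252 | -0.605 | -0.604 | 0.35 |

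Maximum likelihood on all available data, which is what the mixed model delivers, also gives about -0.60 throughout. Within a single trial, complete case and imputation differ on average by only 0.08 at 42% retention and 0.02 at 90%.

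**When the two methods do not agree** (42% retention):

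- Dropout related to baseline HbA1c, log odds ratio +0.5, +1.0 or -0.5 per SD: complete case gives -0.41, -0.25 or -0.80. Imputation stays near -0.60, against a truth of about -0.25. A gap shows, but the imputed result is still wrong.
- Boxes received in the imputation model, gain linear in boxes, dropouts receiving 0 to 4 and completers 6 to 12: imputation gives -0.32 against a truth of -0.33 and a complete-case value of -0.60. Its standard error roughly doubles (0.49 against 0.23).

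**What a delta adjustment does.** Adding 0.6 to each imputed value gives -0.6 + (1 - retention) x 0.6, that is -0.54, -0.48, -0.36 and -0.25 at 90, 80, 60 and 42% retention. The mean t is about -3.5, -2.9, -2.0 and -1.2. At 42%, unadjusted imputation gives about -2.8 and complete case about -2.7.

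**Why exact no-change filling is not a substitute.** At 42% retention it puts a zero in 58 people and shrinks the spread. Variance of change = 0.42 x (2.25 + 0.36) - 0.252^2 = 1.03; SE = sqrt(1.03/100) = 0.102; t = -0.252/0.102 = -2.5. The point estimate moves, but the result remains significant because the uncertainty is understated.

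**Shift that takes the estimated mean to zero** = 0.6/(1 - retention): 6.0, 3.0, 1.5 and 1.03 at 90, 80, 60 and 42% retention. At 42%, dropouts would have to worsen by 1.03 - 0.6 = 0.43 on average.

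**The case against.** The strongest reply is that agreement between the two methods is not a given. The plan leaves the imputation model open, intends to look at predictors of missingness, records reasons for dropout and counts boxes received. An imputation model using those data could expose the problem, as the boxes-received case shows. This stands, and it is why the claim is that the check could mislead, not that it must. It does not remove the point: nothing in the plan commits to those variables, and the favourable case also rests on an extrapolated linear dose effect.

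The second reply is that 42% belongs to a different programme. This also stands. Here boxes are home delivered, outcome data are collected at home or in the community, there is a retention plan, and payment is tied to data collection. A reader might infer that this trial expects to lose more than half its participants; the protocol gives no such forecast. At 80 to 90% retention the bias is small even with zero gain in every dropout.

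Third, a reader might infer that the plan offers agreement as proof of robustness. It does not. It says only that the comparison will examine what missing values could do to the results, and it states no conclusion or decision rule.

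The 10% trigger is a minor matter: at 10% missing, the zero-gain bias is about 0.06 at most.

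**Conclusion.** The concern holds in conditional form. The one stated check compares methods that treat dropouts as responding like completers with the same covariates, so it cannot address dropout that depends on the unseen outcome. If leavers gained nothing and dropout is unrelated to baseline, HbA1c improvement is overstated by about 0.05 to 0.12 points at 80 to 90% retention, 0.24 to 0.25 at 60%, and 0.35 in the 42% stress case.

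A reader might go further and conclude that an apparent benefit would be spurious. The figures do not support that: with zero gain in dropouts, the all-enrolled mean is still a reduction at every retention rate examined. The error is in size. Significance becomes borderline at about 60% retention, is lost on average at 42%, and survives at 80 to 90%. Nor is the bias necessarily towards benefit; that requires leavers to do worse than stayers.

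The same reasoning applies to HEI, but the documents give no expected HEI change or SD, so no size can be stated for it.

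**What to change.** Keep the mixed model as the primary analysis and state that it uses all enrolled participants. Alongside the existing comparison in Data Analysis, pre-specify the following:

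1. A delta-adjusted multiple imputation for HbA1c and HEI, shifting imputed post values in steps towards less benefit, with zero mean gain in dropouts as one named scenario. Report the shift at which significance is lost and whether it is plausible.
2. An imputation model that includes boxes received as well as baseline.
3. A sentence saying that agreement between imputation and complete cases does not rule out informative dropout.

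Do not fill in exact no-change values as a single imputation, because that understates uncertainty.

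The cost is a few lines in SAS, which is already the planned software, and one table; no new data are needed. The downside is a sensitivity result that may look less favourable. This is a cheap improvement.

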Consent materials will be available in English, Spanish, or Marshallese and will use plain language. Eligible participants will be provided a copy of the consent to review, and participants will have the opportunity to ask questions, consent, and enroll in the study. The consent process will include providing information to the potential participants and the opportunity to have bilingual Marshallese or Spanish speaking staff answer questions regarding study participation. The consent document will be given to the participant, and the informed consent process will be documented in the participant's research record. Consent with the participant's signature will serve as documentation. An opportunity will be provided to all potential participants for individual, private discussion of the study and the consent document before they sign the consent. All members of the research team will be trained and certified in participant consent procedures, the study protocol, human subjects protection, and HIPAA regulations.

Enrollment is expected to begin in Year 2 Quarter 3, and will remain open until recruitment goals are met, which is expected to be Year 4 Quarter 2.

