4. Collect data. For each participant, participation will take place over 22 weeks (Weeks 1-4: Pre-intervention data collection; Weeks 5-16: Intervention; Weeks 17-22: Post-intervention data collection). **Table 3** describes the study measures and outcomes. Data collection will take place at pre-intervention and post-intervention for each participant. At enrollment (i.e., pre-intervention) and one week after the 12th food box delivery (i.e. post-intervention), participants will provide data on glycemic control (measured by HbA1c), physical activity, body mass index (BMI), T2D self-management behaviors, T2D knowledge, T2D self-efficacy, and food security. To enhance the study's significance in characterizing the diet patterns and fruit and vegetable consumption of low-income food insecure people with T2D, we are collecting extensive diet quality data measures pre-intervention and post-intervention. Specifically, we will collect 24-hour dietary recalls. Participants will be asked to document their dietary intake over a 24-hour period three times within four weeks. Two of the dietary recalls must be collected from a weekday and one of the recalls must be collected from a weekend day. Also, Skin carotenoid level will be measured using a Veggie Meter® optical skin scanner, which uses Raman Spectroscopy. The Veggie Meter assesses frequency changes in reflected light to calculate carotenoid presence. Skin carotenoid levels are a biomarker of fruit and vegetable dietary

Title: Delivering Health: An Integrated Approach to Address Diabetes in the Context of Food Insecurity

PI: [name]

intake. Participants will be asked to complete a survey via (email, text or in person) asking about their preference for the food provided in the food boxes.

Initial data collection will take place in a private space immediately following enrollment. The remaining pre-intervention data collection and post-intervention data collections will take place via telephone and at locations of each participant's choosing (e.g., HbA1c will be collected at home or at a community-based location such as a food pantry). Our team has necessary expertise and equipment to complete data collection in homes or community-based locations, having successfully completed thousands of such data collection events.^{37,43,54-61}

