The study has a single-arm, pre-post study design. All participants will receive the intervention (i.e., 12 weekly food boxes including the adapted DSME materials). Our target sample size for recruitment is 100. Assuming a repeated measures t-test, two-sided $\alpha=.05$, and a Pearson correlation between repeated measures of $r=.5$, we will have 80% power to detect a Cohen's d effect size of 0.28. For context, Chrvala, Sherr, & Lipman's (2016) meta-analysis found that on average DSME led to a 0.6% improvement in HbA1c.²⁵ Assuming a standard deviation of 1.5%, this translates to Cohen's d of 0.4 (i.e., $0.6/1.5=0.4$). Thus, the proposed intervention with a sample size of 100 is powered to detect a small-to-medium effect consistent with the expected effect size for standard DSME interventions in the context of research trials, and smaller than the effect found in previous food pantry-based DSME interventions.^{33,34}

Table 3. Delivering Health study measures and outcomes	
Variables	Instrument(s) or Measure(s)
COVARIATES	
Demographic & Socioeconomic	Demographic (age, gender, marital status, race, number of adults and children in the household) and socioeconomic (education, employment status, insurance coverage, WIC and SNAP benefits) variables will be captured using validated questions from the Behavior Risk Factor Surveillance System (BRFSS) ⁶² and National Health Interview Study (NHIS). ¹²⁰
EFFECTIVENESS OUTCOMES	
HbA1c	Finger stick blood collection will be used to test HbA1c using a Siemens DCA Vantage analyzer that can be taken into the field. ⁶³
Diet Quality and Fruit and Vegetable Consumption	Skin carotenoid level will be measured using a Veggie Meter® optical skin scanner, which uses Raman Spectroscopy. The Veggie Meter assesses frequency changes in reflected light to calculate carotenoid presence. 24-hour dietary recalls will be collected using the widely-used Nutrition Data System for Research (NDSR) software, which includes over 18,000 foods. ⁶⁴ NDSR will be used to calculate Healthy Eating Index-2015 (HEI) scores and fruit and vegetable consumption. HEI-2015 scores comprise nine

Title: Delivering Health: An Integrated Approach to Address Diabetes in the Context of Food Insecurity

PI: [name]

	component scores (e.g., vegetables, dairy) and are recommended by National Cancer Institute to assess impact of diet quality interventions. ^{65,66}

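### Does adjusting for sex and age, with no season term, leave the single-arm pre-post estimate wrongly analysed?

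*Combined protocol and SAP*

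**What the plan says.** The Data Analysis section makes HbA1c and the HEI-2015 score the primary outcomes and tests pre against post in a repeated-measures mixed model. One sentence then covers adjustment: "Additional analyses will include relevant covariates such as sex or age". It does not say how the covariates enter or what the adjusted models are for. The next sentence adds exploratory models of whether the number of food boxes received predicts change. Earlier in the section, on incomplete data: "If the percentage of missing values is larger than approximately 10%, we will compare models using multiple imputation with those using complete case analysis".

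Item 4 (Collect data) states that "The study has a single-arm, pre-post study design" and that "For each participant, participation will take place over 22 weeks". HbA1c is taken at enrolment and again one week after the twelfth box. The covariates in Table 3 are demographic and socioeconomic; none represents season or calendar date.

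Item 3 (Recruit and enroll) says "Enrollment is expected to begin in Year 2 Quarter 3, and will remain open until recruitment goals are met". The same sentence goes on to forecast that this will happen in the second quarter of Year 4.

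**The concern.** In a single-arm study, anything that shifts the outcome between the two visits is counted as intervention effect. Season is one candidate, since diet and HbA1c may both vary over the year and the visits are about a third of a year apart. The only covariates named for the adjusted models are sex and age, which do not change with season. If they enter as main effects, the adjusted and unadjusted estimates agree by algebra for complete pairs, and a reader could mistake that agreement for robustness. If enrolment did not cover whole years evenly, a seasonal difference could remain in the estimate with no planned analysis to show it.

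**Working it through.** **1. The plan's own figure.** Item 4 gives n = 100, r = 0.5, two-sided alpha 0.05, d = 0.28 and an HbA1c SD of 1.5. The SD of the paired difference is 1.5 × √(2 × (1 − 0.5)) = 1.5. The standard error of the mean change is therefore 1.5/√100 = 0.150, and the detectable change is 0.28 × 1.5 = 0.42. Power is Φ(0.28 × 10 − 1.96) = Φ(0.84) = 80.0% by the normal approximation and 79.2% by the noncentral t. The stated 80% reproduces.

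**2. The algebra.** For person i, write pre = μ + b_i + βx_i + e_i0 and post = μ + δ + b_i + βx_i + e_i1. The difference is δ + e_i1 − e_i0, so βx_i drops out. In one simulated set of 100 complete pairs the mixed model gave −0.384794 both with and without sex and age (SE 0.1435 in both), equal to the raw mean difference. Mean-centred sex-by-time and age-by-time interactions also left the average at −0.384794. With about 20% of post values missing at random, the estimates were −0.3889 without and −0.3885 with the covariates. If loss depends on age, the shift can be larger, and adjusting for it is a legitimate use. So the algebraic statement is right.

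**3. What the plan claims for these models.** The sentence promises additional analyses with relevant covariates. It does not restrict them to main effects, mention time effects or call agreement a robustness check. Its wording gives sex and age as examples, and the dosage sentence already models predictors of change. The algebra therefore contradicts no statement in the plan. What remains is that a season term is not named.

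**4. Season under the forecast window.** Weeks 1–4 precede the intervention and boxes run in weeks 5–16, so HbA1c falls at week 1 and about week 17, a lag of 16 weeks. For an annual cosine of amplitude A and even accrual over D years, the largest bias over phase is

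A × 2 sin(16π/52) × |sin(πD)/(πD)| = 1.646 × A × |sin(πD)/(πD)|.

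Year 2 Quarter 3 to Year 4 Quarter 2 is 2 + 4 + 2 = 8 quarters, so D = 2 if both end quarters are used in full. The documents give no amplitude; 0.1 and 0.2 HbA1c points are assumed.

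| Even accrual over | Factor on A | A = 0.1 | A = 0.2 |
|---|---|---|---|
| 24 months (forecast) | 0 | 0 | 0 |
| 21 months | 0.212 | 0.021 | 0.042 |
| 18 months | 0.349 | 0.035 | 0.070 |
| 27 months | 0.165 | 0.016 | 0.033 |
| 6 months | 1.048 | 0.105 | 0.210 |

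Averaged over phase, the absolute bias is 2/π = 64% of these values. The worst 18-month value, 0.070, is 0.070/0.150 = 0.47 of a standard error and 0.070/0.42 = 17% of the detectable change. A lag of 17 weeks raises the leading constant only from 1.646 to 1.712.

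**5. What a season model would buy.** In simulation, sine and cosine terms cost nothing of note at 24 even months, where there is no bias to remove. At 18 months they multiply the standard error by 1.04 to 1.06. Taking 1.05:

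- A = 0.1: root mean squared error is about √(0.150² + 0.035²) = 0.154 unadjusted and 0.150 × 1.05 = 0.158 adjusted, so adjustment is slightly worse. Simulation gave 0.153 and 0.158.
- A = 0.2: it is about √(0.150² + 0.070²) = 0.166 unadjusted and 0.158 adjusted, so adjustment is modestly better. Simulation gave 0.167 and 0.158.
- Break-even is at √(0.1575² − 0.150²)/0.349 = 0.048/0.349 = 0.14 HbA1c points.

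Power to detect the season terms at 18 to 24 months was only about 10–25% in simulation, so agreement between the two models would say little. If everyone enrolled within half a year, where the bias is large, the standard error roughly doubles (× 1.9 to 2.3) and the model is uninformative.

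**The case for a change.** The strongest case for the concern is that even accrual is nowhere promised, enrolment closes when the target is met rather than on a date, and the protocol describes recruitment under COVID-19 restrictions that might be lifted. Front-loaded accrual over the full 24 months gave a simulated bias of about 0.05 to 0.07 at amplitude 0.2 and worst phase, which sine and cosine terms removed at a 2–5% cost in standard error. A sensitivity model chosen in advance is also better than one chosen after the data are seen, and it need not win on mean squared error to be worth reporting.

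Much of this stands as fact. Seasonal balance is expected rather than guaranteed, no season term is named, and agreement between models with and without main effects of sex and age should not be read as robustness. But these points do not show an error. A recruitment forecast is never a guarantee, the size rests on an assumed amplitude set at its worst phase, and the plan claims nothing that the algebra refutes. For HEI-2015 the effect cannot be sized, because the documents give no SD.

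Season is also not the main limit of this design. With the entry rule "HbA1c levels of ≥ 7" and an assumed underlying mean of 8, a true change of −0.60 appeared as −0.92 in simulation, and as −0.92 again with season terms added. That 0.32 is regression to the mean, a separate matter that a season model leaves untouched.

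**Conclusion.** The concern does not hold. Fixed covariates do drop out of a complete-pair contrast, but the plan assigns the sex and age models no purpose that this defeats, and it leaves both their form and the covariate list open. Under the forecast eight quarters with even accrual, the bias from an annual cycle is zero. Plausible departures give roughly 0.02 to 0.07 HbA1c points against a standard error of 0.150 and a detectable change of 0.42. Those figures assume an amplitude of 0.1 to 0.2 points, the worst phase, and a shorter or uneven enrolment that the documents do not describe. Larger bias needs enrolment concentrated in about half a year, where a season model could not help. Adding season terms is a reasonable preference, but their absence is not a defect.
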